### **8.8.2. Exploratory Analyses Evaluating Effect of Reldesemtiv**

To characterize the effect of reldesemtiv, additional comparisons will be conducted based on delayed-start design features.

- The early-start treatment group includes patients who are randomized to receive reldesemtiv. Patients in this group are to receive reldesemtiv during both double-blind, placebo-controlled period and active drug period for a total of 48 weeks.
- The delayed-start treatment group includes patients who are randomized to receive placebo. Patients in this group are to receive placebo during the double-blind, placebo-controlled period for 24 weeks, and then switch to receive reldesemtiv during the active drug period for 24 weeks.

Comparisons listed below will be performed to evaluate treatment differences in 1) change of ALSFRS-R total score from baseline, and 2) combined assessment of change of ALSFRS-R, dependence on assisted ventilation (either invasive or non-invasive), and survival time.

- Compare changes from Week 24 to Week 48 between the early-start and delayed-start treatment groups
- Compare changes from baseline to Week 48 between the early-start and delayed-start treatment groups

- Compare changes from Week 24 to Week 48 versus those from baseline to Week 24 in the delayed-start group

The analysis will include all data collected up to Week 48 (including data from the patients who discontinued the study treatment early but remained in the study and had data being collected). The analysis will also be conducted for patients who were on treatment (ie, excluding data collected after the discontinuation of the study treatment).

### **8.9. Summary of Reasons for Efficacy Non-Evaluability/Exclusion from Efficacy Analyses**

Efficacy analyses will be performed based on the FAS. Reason of excluding patients from the FAS will be summarized or listed.

## **9. SAFETY AND TOLERABILITY**

Safety and tolerability analyses will be based on the Safety Analysis Set. Safety data will be analyzed descriptively and tabulated by the early-start and delayed-start treatment groups for the double-blind placebo-controlled period and active drug period).

### **9.1. Overall Summary of Tolerability**

Overall summary of tolerability will include the following:

- Number of patients treated and patient years of drug exposure (mean, min, max, and median)
- Number of patients with treatment-emergent adverse events (TEAEs)
- Number of patients with treatment-emergent serious adverse events (TESAEs)
- Number of patients with TEAEs leading to permanent dose reduction
- Number of patients with TEAEs leading to premature treatment discontinuation
- Number of patients with TEAEs leading to premature study discontinuation
- Number of Deaths

### **9.2. Adverse Event Preferred Term and Body/Organ System Summary Tables**

#### **9.2.1. Summaries of Adverse Event Incidence Rates for All Subjects**

All AE terms will be coded using the Medical Dictionary for Regulatory Activities (MedDRA). TEAEs and TESAEs will be summarized by primary SOC and PT, by PT, and also by severity (Grades 1 to 5) and relationship to study drug (related and not related). For a TEAE reported more than once from a patient, the TEAE will be counted only once in the SOC or PT category using the most severe occurrence and/or closer relationship to the study drug. All AEs will be listed.

#### **9.2.2. Missing and Partial AE Onset Dates**

For AEs with incomplete date information recorded on the eCRF, imputation will be performed following the algorithm below:

For missing AE onset Day and Time:

- If an AE onset Day is missing and the Month of AE onset is known, then the first day of the month of AE onset will be imputed as the AE onset date.
- If AE onset information is not available, then the first dosing date will be imputed as the AE onset date.

For missing AE end Day and Time:

- If the AE end Day is missing and the AE end Month is earlier or later than that of the Follow-Up Visit, then the last day of the AE end month will be the imputed as the AE end date.
- If the AE end Day is missing and the AE end Month is the same as that of the Follow-Up Visit, then the date of the Follow-Up Visit will be the imputed as the AE end date.
- If no AE end information is available, then
  - For patients who discontinued early from study drug, the imputed AE end date will be on the later of the last dosing date + 28 days or the last visit or contact date.
  - For patients who completed the study, the imputed AE end date and time will be the date of the Follow-Up Visit.
  - If the stop date is missing and the event is ongoing, the event will be noted as ongoing” in the stop date column in data listings.

### **9.2.3. Summaries of Adverse Incidence Rates for Serious Adverse Events (SAE), Adverse Event Dropouts, and Death**

Serious Adverse Events (SAEs) and AEs leading to premature treatment or study discontinuation and death will be summarized by SOC and PT, and by PT. Listings will be presented for patients who died and/or experienced serious AEs and for patients who discontinued prematurely due to TEAEs.

### **9.2.4. Summaries of Adverse Events of Special Interest**

The following events are considered adverse events of special interest:

- Manifestations of renal impairment and toxicity defined in the protocol Section 7.3, including clinically significant decreases in eGFRCysC and increases of urine protein creatinine ratio
- Clinically significant elevated transaminases and/or bilirubin and manifestations of liver toxicity defined in the protocol Section 7.4 (eg, rash, abdominal pain, nausea and vomiting, fatigue, dark-colored urine, light-colored bowel movements, jaundice, loss of appetite, fever)

Adverse events of special interest recorded on the CRF will be summarized by SOC and PT. Patients with adverse events of special interest and their laboratory values will be listed.

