6.3. Measures to Minimize Bias: Randomization and Blinding

All patients will be centrally assigned to randomized study drug using an Interactive Web Response System (IWRS). Before the trial is initiated, the log in information & directions for the IWRS will be provided to each site.

Study drug will be dispensed at the study visits summarized in the SoA ([Section 1.3](#)). Returned study drug should not be re-dispensed to the patients.

The IWRS will be programmed with blind-breaking instructions and the unblinding procedure is documented in the IWRS User Manual. In case of an emergency, the investigator has the sole responsibility for determining if unblinding of a patient's treatment assignment is warranted. Patient safety must always be the first consideration in making such a determination. If the investigator decides that unblinding is warranted, the investigator should make every effort to contact Cytokinetics prior to unblinding a patient's treatment assignment unless this could delay emergency treatment of the patient. If a patient's treatment assignment is unblinded, Cytokinetics must be notified within 24 hours after breaking the blind. The date and reason that the blind was broken must be recorded in the source documentation and CRF, as applicable.

An unblinded physician (unmasked to renal labs but blinded to treatment assignments) who is not on the study team may direct a study drug interruption and a down-titration of patients based upon review of unmasked renal function laboratory values that meet the prespecified criteria ([Section 6.6](#) and [Section 7.3](#)). In order to preserve blinding of site staff and the study operation team, a small number of placebo patients will be selected for dummy down-titration during the study by the unblinded Clinical Research Organization (CRO) physician and will undergo repeat laboratory testing similar to what could be directed for patients receiving active treatment with laboratory abnormalities. The blinded down-titration selection criteria and records will be documented by the unblinded physician and the unblinded statistician separately. In order to maintain the blind, placebo patients who had a dummy down-titration during the double-blind dosing period will take 150 mg bid of reldesemtiv during the active drug period.

The randomization treatment assignments for individual patients will remain blinded to site staff and patients until the entire study is completed and the database is locked.

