To accomplish this, the unblinded physician may direct the laboratory assessments (serum cystatin C, eGFR_{CysC}, serum creatinine eGFR_{Cr}, UPCR) to be repeated as often as 2-3 times weekly until a final disposition is reached (ie, re-initiation of study drug or placebo at 150 mg bid or permanent discontinuation) is reached.

Manifestations of renal toxicity, including clinically significant decreases in eGFR_{CysC} and eGFR_{Cr}, as well as increases of UPCR, as noted above, are considered adverse events of special interest and should be recorded on the appropriate CRF and reported to Cytokinetics Drug Safety within 24 hours of awareness.

Criteria for permanent discontinuation of study drug due to potential renal toxicity

Study drug **must** be discontinued permanently if the patient requires hemodialysis.

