8.3. Adverse Events and Serious Adverse Events

8.3.1. Adverse Events

8.3.1.1. Definition of Adverse Event

An AE is defined as any untoward medical occurrence in a patient or clinical investigation patient administered a pharmaceutical product and which does not necessarily have a causal relationship with this treatment. An AE can therefore be any unfavorable and unintended sign (including an abnormal laboratory finding), symptom, or disease temporally associated with the use of study drug, whether or not related to study drug.

Adverse events include:

- Exacerbation of a chronic or intermittent pre-existing condition including either an increase in frequency and/or intensity of the condition.
- New conditions detected or diagnosed after IP administration even though it may have been present before the start of the trial.

- Abnormal assessments, eg, change on physical examination, ECG findings, if they represent a clinically significant finding that was not present at trial start or worsened during the course of the trial.
- Laboratory test abnormalities if they represent a clinically significant finding, symptomatic or not, which was not present at trial start or worsened during the course of the trial, require treatment, or led to dose reduction, interruption or permanent discontinuation of IP. In general, abnormal laboratory findings without clinical significance (based on the investigator's judgment) are not to be recorded as adverse events. Where applicable, clinical sequelae (not the laboratory abnormality) are to be recorded as the adverse event.
- Signs, symptoms, or the clinical sequelae of a suspected drug-drug interaction.
- Signs, symptoms, or the clinical sequelae of a suspected overdose of either study drug or a concomitant medication. Overdose per se will not be reported as an AE/SAE unless it is an intentional overdose taken with possible suicidal/self-harming intent. Such overdoses should be reported regardless of sequelae.

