**Reference therapy, dose and mode of administration:**

Matching placebo will be administered as tablets, at a dose of 2 tablets twice a day. Matching placebo tablets will be taken orally.

In order to maintain the blind to site staff and the study operation team, a small portion of placebo patients will be randomly selected for down-titration to 1 tablet twice a day during the study by the CRO physician unblinded to the renal laboratory results.

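### The SAP has no rule separating dummy renal down-titrations in placebo patients from real ones, so its descriptive renal AE and dose-reduction outputs are likely to be biased towards no difference

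*SAP*

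**What the plan says.** Protocol 6.3 states that "a small number of placebo patients will be selected for dummy down-titration during the study", and that these patients "will undergo repeat laboratory testing similar to what could be directed for patients receiving active treatment with laboratory abnormalities". It adds that the selection criteria and records "will be documented by the unblinded physician and the unblinded statistician separately". The SAP mentions the device once, in its technical summary: "a small portion of placebo patients will be randomly selected for down-titration to 1 tablet twice a day". Neither document gives a number.

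Under Protocol 7.3 the sites, the sponsor and the medical monitors do not see creatinine, cystatin C, either eGFR, or UPCR. A physician outside the study team reviews those results and contacts the site when the hold criteria are met.

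On recording, Protocol 7.3 says that manifestations of renal toxicity "are considered adverse events of special interest and should be recorded on the appropriate CRF", with notice to the sponsor's drug safety group within 24 hours. Protocol 8.3.1.1 counts a laboratory abnormality as an AE if it is clinically significant and, among other conditions, "or led to dose reduction, interruption or permanent discontinuation of IP". Protocol 6.4 puts dose reductions on the CRF.

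On analysis, SAP 9.2.4 says: "Adverse events of special interest recorded on the CRF will be summarized by SOC and PT". The tolerability overview in SAP 9.1 includes "Number of patients with TEAEs leading to permanent dose reduction". SAP 9.3 lists dose reductions with their reasons, and SAP 8.6.2 splits the primary endpoint by down-titration, yes or no.

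**The concern.** A dummy procedure protects the blind only if the site cannot tell it from the real thing, and the site's CRF entries are the source for the AE tables. A site that is told by the renal physician to down-titrate, and then to repeat renal tests it cannot read, has good reason to take the instruction as renal. It may then enter a renal AE and an AE of special interest (AESI) for a placebo patient with normal kidneys.

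Every such record sits in the placebo arm. The AESI incidence and the count of TEAEs leading to permanent dose reduction would then understate the excess on reldesemtiv. Renal effects are one of the two laboratory safety risks for which Protocol 2.3.1.1 sets out a mitigation strategy. The AE tables could also disagree with the laboratory tables, with nothing in the SAP to explain the disagreement.

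**Working it through.** **1. Which outputs depend on a site entering an AE?**

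- SAP 9.2.4 AESI table: yes. It takes what is on the CRF.
- SAP 9.1 count of TEAEs leading to permanent dose reduction: yes. It needs a TEAE as the cause.
- SAP 9.3 dose-reduction listing: no. The reduction is on the CRF regardless.
- SAP 8.6.2 down-titration subgroup: no. A comparison within the yes stratum needs placebo patients in it. Those would be dummy cases together with any placebo patients reduced by the investigator for an AE.
- SAP 9.5 eGFR change, categories and shifts: unaffected. A dummy instruction does not alter a measured value.

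**2. Does any analysis section use the dummy log?** No. The SAP's only mention is descriptive, in its summary.

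**3. Does a planned table replace the AESI count?** Not fully. SAP 9.5 tabulates cystatin C eGFR, including a category of 15 to <30. The Protocol 7.3 hold rule is both eGFRs below 30.0, or UPCR of at least 3 mg/mg. No table counts patients meeting it.

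**4. Arm sizes.** Inputs from Protocol 9.2: difference 1.8, SD 5.5, two-sided alpha 0.05, power 90%, 2:1.

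Placebo n = 1.5 × (1.960 + 1.282)² × 5.5² / 1.8² = 147.1, rounded up to 148. The total is 3 × 148 = 444, which matches the stated evaluable number, and 444 / 0.80 = 555 reproduces the planned size. The split is 370 reldesemtiv and 185 placebo.

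**5. Effect of each recorded dummy.** 1/185 = 0.54 points added to the placebo rate.

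**6. Number of dummies that cancels the difference** = (true reldesemtiv rate − placebo background) × 185.

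The documents give no true trigger rate, so a range is assumed. One anchor is Protocol 2.3.1: 7/457 = 1.53% of CY 5022 participants stopped drug for a decline in cystatin C eGFR. If all seven were on reldesemtiv, which is not stated, the denominator is about 24/0.070 = 343 (from the transaminase figures in the same section), giving 2.04%.

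| Assumed true rate | Expected of 370 | Dummies to cancel, background 0 | Dummies to cancel, background 0.5% |
|---|---|---|---|
| 1.0% | 3.7 | 1.9 | 0.9 |
| 1.53% | 5.7 | 2.8 | 1.9 |
| 2.04% | 7.6 | 3.8 | 2.9 |
| 4.0% | 14.8 | 7.4 | 6.5 |

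At 1.53% with zero background, the apparent difference is 1.53 points with no dummies recorded, 0.99 with one, 0.45 with two and −0.09 with three.

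**The case against.** The strongest reply is that the documents do not show that a dummy becomes an AE. Protocol 7.3 confines renal AESI to manifestations of toxicity, and Protocol 8.3.1.1 requires a clinically significant finding. A dummy patient has neither. Nothing states what the site is told, or what reason it records. Protocol 6.3 describes similar repeat testing; it does not say that the site hears that the hold criteria were met. Sites are also not wholly in the dark, because urea nitrogen, potassium and urine microscopy are collected and are not on the masked list. A reader might infer that sites must enter a renal event for each dummy. The documents do not support that.

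This stands, and it limits the claim to likely. It does not remove it. The site cannot check the abnormality on which both rules turn, neither rule exempts dummies, and a standing instruction not to record them would mark those patients as placebo.

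The second reply is that other protections exist. Safety analysis is descriptive, measured eGFR is summarised in several ways, SAP 9.2.4 lists laboratory values for AESI patients, and the DMC sees treatment assignments and includes a nephrologist. All true. But a listing does not correct an incidence table.

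The third reply is that 7/457 is a poor proxy. It counts treatment terminations across all CY 5022 arms, including placebo and 450 mg twice daily, whereas the trigger here is a different event at 300 mg twice daily. That also stands, which is why a range is shown.

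A reader might also infer false expedited reports to regulators. The 24-hour rule in Protocol 7.3 is notice to the sponsor; Protocol 8.3.1.9 ties regulatory reporting to serious events and reactions.

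**Conclusion.** The gap in the SAP is established: no analysis section separates dummy from real down-titrations, although a record of the dummies exists. The SAP 9.3 listing and the SAP 8.6.2 subgroup mix the two in any case. Contamination of the SAP 9.2.4 and 9.1 counts is likely but not certain. If it occurs, it is confined to placebo and biases the contrast towards no difference.

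The size cannot be fixed from the documents. It is 0.54 points per recorded dummy. About 3 would cancel an assumed true rate of 1.5%, and 7 to 8 would cancel 4%, with zero placebo background and every dummy recorded as an AESI. A 0.5% background lowers each figure by about one.

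A reader might go further and conclude that the trial's main renal safety comparison is nullified or reversed. That does not follow. The measured eGFR summaries stand, no test is planned, and a reversal needs assumed dummy counts, an assumed true rate and universal recording.

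**What to change.** Before database lock, add to SAP 9.1, 9.2.4, 9.3 and 8.6.2:

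- How a dummy down-titration is recorded on the CRF.
- That the dummy-selection log is merged with the AE and dosing data at unblinding. Protocol 6.3 has the physician and the statistician keep records separately, so the two should be reconciled first.
- That AE, AESI and dose-reduction records triggered by a dummy instruction are flagged, not deleted, and that the AESI, dose-reduction and down-titration outputs are shown with and without them. Flagging keeps any genuine symptom in a dummy patient in view.
- A table by arm of patients whose central laboratory values meet the Protocol 7.3 hold criteria, so that the comparison does not depend on what blinded sites entered.

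Two wordings on how dummies are chosen should be reconciled at the same time. The SAP says selection is random while Protocol 6.3 refers to selection criteria. Protocol 6.3 also calls the physician blinded to treatment assignment yet has that physician pick placebo patients.

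The cost is one merge, a few extra tables and a written rule for attributing a record to the dummy instruction. That rule involves some judgement, so it should be fixed in advance: setting placebo-only renal events aside after unblinding without one would look selective. No treatment rule changes, and the blind is untouched because the merge happens at unblinding.

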### **9.3. Total Duration of Therapy, Average Daily Dose, Maximum Daily Dose, Final Daily Dose of Study Medication, and Compliance**

Total duration of treatment and exposure of study drug per day will be summarized. All doses taken, date/time of dose, dose reduction (yes/no) and reason of dose reduction will be listed.

## 9.4. Concomitant and Other Medications

Concomitant medications reported on the eCRF will be summarized. Medications with a start date that is 28 days after the last dose of the study drug will be excluded from the summary. The WHO Drug Dictionary will be used to classify medications by therapeutic class (ATC Class 3) and preferred name. If ATC Class 3 is not available, ATC Class 2 will be used in the summary. Coding will be performed using WHO Drug Dictionary Enhanced with Herbal Dictionary, B3, SEP 2020.

CYP3A4 strong inhibitors should be avoided from 7 days before the start of dosing through the last day of dosing. CYP3A4 strong inducers should be avoided from 14 days before the start of dosing through the last day of dosing. OCT1/OCT2 substrates should be avoided from 7 days before the start of dosing or should be used with caution during the study. Patients who take CYP3A4 strong inhibitors, CYP3A4 strong inducers, or OCT1/OCT2 substrates prior or during the study treatment will be listed.

Concomitant medications taken throughout the study will be listed. The listing will include concomitant medication, start/stop date, study day, dose / unit / route / frequency, indication and purpose of concomitant medications.

### 9.4.1. Missing and Partial Concomitant and Other Medication Start and Stop Dates

Incomplete concomitant medication start and/or stop dates will be imputed as follows. If either the start of medication date is completely missing or the month and/or year of the start date is missing, the start date will be set to the first dose date. If only the day is missing, the day will be set to the first day of the month except if the start month is the same as the first dose month. If the latter is true, the start day will be set to the first dose day. No imputations will be applied to the stop date.

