6.5. Concomitant Therapy

Any medication, including over-the-counter or prescription medicines, vitamins, and/or herbal supplements, that the patient is receiving at the time of enrollment or receives during the trial must be recorded along with:

- Reason for use
- Dates of administration including start and end dates
- Dosage information including dose, frequency and route of administration

The Medical Monitor should be contacted if there are any questions regarding concomitant or prior therapy.

Patients may continue to take prescription medications and non-prescription medications which in the opinion of the investigator and the Medical Monitor, will not interfere with the trial.

During the trial, medications and doses should remain stable whenever appropriate. However, investigators may prescribe or adjust any concomitant medication or treatment deemed necessary to provide adequate supportive care.

Prior use of riluzole, edaravone and the combination product (brand name only) of sodium phenylbutyrate and taurursodiol, even if stopped prior to screening, will be recorded along with the reason why it was stopped (patient choice, adverse event, cost). Patients should neither stop nor start edaravone, riluzole or the combination product of sodium phenylbutyrate and taurursodiol following randomization. However, it is recognized that changes in medications may occur including those due to the development of adverse events potentially related to these medications or changes in insurance coverage. Patients who start or stop edaravone, riluzole and the combination product (brand name only) of sodium phenylbutyrate and taurursodiol following randomization will be permitted to continue in the trial.

Drug-Drug Interactions

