### **6.8.2. Missing Start and Stop Dates for Prior and Concomitant Medication**

Imputation of missing/partial dates will not be performed. The available year or year and month in a partial date will be used and will be compared to first dosing year, month and day to determine whether to include the medication in the medication history or as a concomitant medication. If the available data do not give sufficient information to classify the medication, the medication will be classified as concomitant medication.

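### SAP 6.8.2 and SAP 9.4.1 give contradictory rules for partial medication dates, and 9.4.1 replaces a recorded start year with the first dose date

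*SAP*

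**What the plan says.** SAP 6.8.2, whose heading covers prior and concomitant medication, states: "Imputation of missing/partial dates will not be performed". It then says how partial dates are to be used: "The available year or year and month in a partial date will be used and will be compared to first dosing year, month and day", in order to place the drug in the history or among concomitant medications. Its fallback is: "If the available data do not give sufficient information to classify the medication, the medication will be classified as concomitant medication".

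SAP 9.4.1, whose heading covers concomitant and other medication, opens the other way: "Incomplete concomitant medication start and/or stop dates will be imputed as follows". If the start date is wholly missing, or "the month and/or year of the start date is missing, the start date will be set to the first dose date". For a missing day alone: "If only the day is missing, the day will be set to the first day of the month except if the start month is the" first-dose month, when the first dose day is used. It closes with "No imputations will be applied to the stop date", although its opening sentence announced imputation of stop dates too.

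Neither section refers to the other or says which prevails. SAP 9.4 requires a concomitant medication listing with start and stop dates and study day, and leaves out of the summary medications that start 28 days after the last dose. SAP 6.7.2 makes the first dose date Study Day 1.

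**The concern.** A programmer who follows either section departs from the other. The conflict also matters in substance, because 9.4.1 overrides information that was collected. When the year is known and the month is not, the record often shows already which side of first dose the drug started on. Section 6.8.2 uses that; 9.4.1 throws it away and writes in the first dose date.

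Such records are foreseeable. Protocol 5.1 requires riluzole users to have been on the drug for at least 30 days before screening, so a Day 1 start for a baseline user would be false by the trial's own criteria. Protocol 6.5 has prior use of the three ALS therapies recorded even when stopped before screening. It also says: "Patients should neither stop nor start edaravone, riluzole or the combination product of sodium phenylbutyrate and taurursodiol following randomization". A listing that shows background ALS therapy starting on Day 1 invites misreading against that instruction.

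At stake are the accuracy of the medication history and concomitant medication outputs (SAP 7.7 and 9.4) and the internal consistency of the listed dates.

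**Working it through.** The plan gives no figure to reproduce. The check applies both rules, as written, to the same records.

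**Inputs.** The rules come from SAP 6.8.2 and 9.4.1. Study day comes from SAP 6.7.2: date minus first dose, plus 1 if on or after first dose; date minus first dose if earlier. The first dose date (20 Mar 2022) and all medication dates are assumptions for illustration.

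| Recorded start | Recorded stop | 9.4.1 start (study day) | Stop (study day) | 6.8.2 |
|---|---|---|---|---|
| 2020, month unknown | ongoing | 20 Mar 2022 (1) | none | started before first dose |
| 2020, month unknown | 15 Jun 2021 | 20 Mar 2022 (1) | −278 | history |
| wholly missing | 15 Jun 2021 | 20 Mar 2022 (1) | −278 | start alone is uninformative; the stop date, if used, gives history |
| Mar 2022, day unknown | 10 Mar 2022 | 20 Mar 2022 (1) | −10 | start alone is uninformative; the stop date, if used, gives history |
| 2023, month unknown | ongoing | 20 Mar 2022 (1) | none | started after first dose |
| wholly missing | ongoing | 20 Mar 2022 (1) | none | concomitant by default |
| May 2020, day unknown | ongoing | 1 May 2020 (−688) | none | started before first dose |

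**Row 1: a recorded earlier year is overridden.** From 1 Jan 2020 to 20 Mar 2022 is 366 + 365 + 78 = 809 days. From 31 Dec 2020 it is 809 − 365 = 444 days. The true start lies between Study Day −809 and −444, and 9.4.1 lists Day 1.

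**Rows 2 to 4: a start can follow its stop.** In rows 2 and 3 the imputed start is 278 days after the stop (15 Jun 2021 to 20 Mar 2022). In row 4 it is 10 days after. Section 9.4.1 has no check against the stop date. This result needs three things together: an incomplete start, a recorded stop before first dose, and 9.4.1 being applied to that record.

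**Row 5: a recorded later year is overridden.** Suppose this patient's last dose was 30 Jun 2022. The earliest start compatible with 2023 is 1 Jan 2023, which is 31 + 31 + 30 + 31 + 30 + 31 + 1 = 185 days later, well past the 28-day limit in SAP 9.4. Section 9.4.1 dates the start to 20 Mar 2022, so the drug enters a summary that should exclude it.

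**Rows 6 and 7: no conflict in result.** With nothing known about the start and the drug ongoing, both sections lead to concomitant. With only the day missing in an earlier month, 9.4.1 stays within the recorded month and agrees with 6.8.2 on which side of first dose the drug started.

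**The case against.** The best defence is that the sections do different jobs in sequence: 6.8.2 classifies, and 9.4.1 then supplies dates for drugs already classed as concomitant. The body of 9.4.1 does speak of concomitant medication, and it classifies nothing itself. On that reading a drug with a known stop before first dose is history and never reaches 9.4.1, so no start falls after a stop in rows 2 to 4.

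This has force against the start-after-stop result, which is possible and not certain. It does not remove the contradiction: the ban in 6.8.2 is unqualified, no sequence is stated, and the 9.4.1 heading extends to other medication. Nor does it help rows 1 and 5, where a drug that is concomitant on any reading still has its recorded year overwritten.

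A reader might infer wider harm. The documents do not support the following:

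- **Baseline riluzole or edaravone use miscoded in the primary model.** Both are randomisation stratification factors (SAP 4.4), and nothing derives them from imputed medication dates.
- **A changed list of patients taking CYP3A4 or OCT1/OCT2 drugs.** SAP 9.4 lists use before or during treatment, so who is listed does not turn on this date. Only a displayed date could be wrong.
- **A corrupted check on post-randomisation starts of ALS therapy.** Neither document specifies such a check from these dates, and Protocol 6.5 lets patients who start or stop continue.
- **A large number of affected records.** It is tempting to say that chronic drugs are usually recorded by year only, but the documents do not say so. Protocol 6.5 asks for start and end dates.

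The date rule is also the same in both arms.

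**Conclusion.** Wrong as written, minor severity. The contradiction is certain: it rests on the text of two sections whose headings both cover concomitant medication. It is also certain that 9.4.1, followed literally, replaces a known earlier or later start year with the first dose date. Whether a start falls after a stop depends on whether 9.4.1 is applied to drugs stopped before first dose, which the text leaves open.

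The reach is limited to descriptive medication tables, listings and study day. No endpoint, hypothesis test or safety conclusion is shown to depend on it. The share of affected records cannot be derived from the documents, and the worked dates show direction and mechanism only.

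**What to change.** State one rule and have both sections refer to it:

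1. Classify each drug as history or concomitant from the known parts of its dates, as 6.8.2 does. Say that a recorded stop before first dose makes it history.
2. Where a full date is needed for study day, impute within the recorded year, or year and month. A recorded year before first dose stays before it, and a later year stays after it.
3. Use the first dose date only when the known parts are compatible with it.
4. Never set a start later than a recorded stop date.
5. Correct the opening sentence of 9.4.1, since stop dates are not imputed.

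Deleting 9.4.1 outright is the simpler edit, but study day could then not be computed for partial dates in the required listing. The conditional rule avoids that.

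The cost is SAP wording and one derivation, settled before database lock. No data collection changes and no efficacy programming is touched.
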